Date last updated: October 24, 2024 Date v1.0 implemented: January 1, 1986 UCSF IRB: 21-35637 WHO Protocol ID: ERC.0004026

Protocol: Basic pulse oximeter hypoxemia (lab) performance study

Citation: UCSF Hypoxia Lab, Protocol for basic pulse oximeter hypoxia performance study. May 2024. https://openoximetry.org/study-protocols/

Abstract/Description

Pulse oximeters were introduced clinically around 1982 and are routine in most clinical settings including surgery, recovery, intensive care, and other special applications where patients may be at risk of inadequate oxygenation or ventilation. There are numerous manufacturers of these devices. The instruments intended for clinical use are required by the US FDA and multiple other bodies to be tested per ISO 80601-2-61 over the range of SpO2 70-100%. The instruments are calibrated by design at the factory and generally do not need or permit recalibration.

This study protocol was started in 1986 to determine the performance of pulse oximeters and to help generate data to improve performance and safety. More than 3000 subjects have been studied, using more than 100 different manufacturers' devices. Because of continuing improvements in pulse oximeter design, continuing introduction of new products to the market, and ongoing challenges in performance, the testing is still needed to ensure and improve safety and performance of pulse oximeters.

Update history

October 24, 2024 - Updated sampling to more accurately describe practice of blood gas sample analysis

September 26, 2024 - Updated Section 4 to specify that all fingers on either hand, including in the presence of an arterial line, are used to test pulse oximeter performance. Also updated our timing for achieving plateau stability

June 10, 2024 - Removed methylene blue as an exclusion criteria

May 28, 2024 - Updated Step 1 of the protocol to include our recruitment practices (i.e. use of the UCSF Clinical and Translational Science Institute (CTSI) Participant Recruitment Program (PRP), TrialFacts as well as other general recruitment strategies). Other minor edits to the steps were made to reflect the current practices of the Hypoxia Lab in terms of arterial line insertion, blood sampling, assessing participants' vital signs, control of the gas mixtures, etc.

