- c. SaO2 and SpO2 data from the reference devices (Nellcor PM1000N and Masimo Rad-97) are cleaned using an algorithm that checks for plateau stability. Data points are flagged if their difference from both the previous and next readings exceeds a predefined threshold. If the data point is the first or last in the session, the difference from the subsequent or preceding reading, respectively, will be checked. The threshold for flagging SaO2 data points is 1.5, while the threshold for SpO2 data from the references is 2. Any data point flagged for either SaO2 or SpO2 from Nellcor PM1000N will be excluded from the analysis and undergoes manual review.
- d. Finally, sessions will be flagged for review if they contain at least one data point from devices under test that meets any of the following criteria: 1) an absolute bias greater than 20, 2) a bias difference of ≥5 compared to both the previous and next samples, or 3) an SaO2 value of 80% or higher with an absolute bias greater than 10. Flagged sessions will be reviewed manually by the Principal Investigator, and data points will be excluded based on their

instructions. These criteria were determined after manual analysis of >600 sessions (>10,000 data points).

- e. For some studies, sponsors may request to record the subject's face during the desaturation study. These recordings will be used to determine if blood oxygen saturation can be determined through facial recordings. These recordings will be kept by the sponsor for a period of 2 years after completion of the study. Timestamps will be used to correlate to the subject number.
- f. For some studies, the protocol may video record the hands and/or wrists through the study period. This is to record data from pulse oximeters with displays on the wrist and hands (i.e. to record the data output directly from the display). This information would be kept by sponsors/investigators for the length of the IRB approved period. The subject faces would not be recorded at any point for this purpose. Timestamps from the video recording will be used to correlate video recordings to the subject number.

[figure not shown]
Device Calibration

- 1. Konica Minolta
 - a. Device undergoes yearly factory calibration.

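### Item 13d flags readings by the test device's own bias and lets points be excluded with no stated ground, so a reading can leave the accuracy analysis because its error is large

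*Protocol*

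**What the plan says.** The Abstract/Description gives the purpose: "This study protocol was started in 1986 to determine the performance of pulse oximeters". Under Study Design, item 8a, readings from the test oximeters are compared with SaO2 measured by co-oximetry. The difference between the two, the bias, is therefore the outcome.

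Item 13d is the last cleaning step. It says that "sessions will be flagged for review if they contain at least one data point from devices under test that meets any of the following criteria". The criteria are:

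1. absolute bias above 20;
2. "a bias difference of ≥5 compared to both the previous and next samples";
3. "an SaO2 value of 80% or higher with an absolute bias greater than 10".

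The consequence is: "Flagged sessions will be reviewed manually by the Principal Investigator, and data points will be excluded based on their" instructions. The sentence runs over a page break and ends with that one word, so no ground is lost in the break. On the origin of the criteria, 13d adds: "These criteria were determined after manual analysis of >600 sessions (>10,000 data points").

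Two other rules exclude individual samples. Item 8a drops a blood sample when no two of three analyser results agree within 0.5%. Item 13c applies stability thresholds of 1.5 for SaO2 and 2 for reference SpO2, and says: "Any data point flagged for either SaO2 or SpO2 from Nellcor PM1000N will be excluded from the analysis and undergoes manual review".

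**The concern.** In an accuracy study a large error of the test device is a result. It may also be an artefact, such as a displaced probe or a transcription slip, and removing an artefact is proper cleaning. The size of the bias alone does not tell the two apart. Item 13d uses the bias to raise the flag and asks for nothing further before a point is excluded. Where the excluded reading is true device error, the reported accuracy is better than the device's real accuracy. Because no reason has to be given, a reader of the results could not tell which kind of reading was removed.

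**Working it through.** **Step 1. What drives each exclusion.**

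| Rule | Quantity used | Test for exclusion |
|---|---|---|
| 8a | SaO2 on two or three analysers | No two results within 0.5% |
| 13c | SaO2 and Nellcor reference SpO2 against neighbouring readings | Change above 1.5 (SaO2) or 2 (SpO2) |
| 13d | Bias of the device under test | The Principal Investigator's instructions; no test stated |

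The first two rules cannot depend on how the test device performed. The third depends on it through all three criteria. No other section supplies a ground for exclusion under 13d.

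**Step 2. Direction.** Let M be the mean squared error over n points. Removing a point with bias b changes M to (nM − b²)/(n − 1), which is smaller than M exactly when |b| exceeds the RMS error, √M.

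- Criteria 1 and 3 select |b| above 20 or above 10. For any device with RMS error below 10, removing such a point improves the figure.
- Criterion 2 carries no such guarantee. Successive biases of +6, +1 and +6 differ by 5 and 5, so the middle reading meets the criterion although it has the smallest error of the three.

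**Step 3. Size, as an illustration only.** The protocol states no accuracy metric, no accuracy limit and no number of exclusions, so there is no figure of its own to reproduce. Assumptions: RMS error is the metric, the retained points have RMS 3.0, and k points are excluded, each with absolute bias b = 10.1 (just over 10) or b = 20.1 (just over 20).

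Number of points n:
- 24 participants (item 1a) × 10,000/600 ≈ 16.7 points per session (13d) = 400. Both 13d counts are lower bounds and may pool devices.
- 24 × 30 = 720, using the maximum of 30 samples in item 8a.
- 100 × 30 = 3,000, for the larger cohorts in item 1a.

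RMS before exclusion = √{[(n − k) × 9 + k × b²]/n}.

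For n = 400:
- k = 1, b = 10.1: √[(399 × 9 + 102.01)/400] = √9.233 = 3.04
- k = 1, b = 20.1: √[(399 × 9 + 404.01)/400] = √9.988 = 3.16
- k = 5, b = 10.1: √[(395 × 9 + 510.05)/400] = √10.163 = 3.19
- k = 5, b = 20.1: √[(395 × 9 + 2,020.05)/400] = √13.938 = 3.73

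After exclusion the RMS is 3.00 in every case.

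| n | RMS before excluding 1 point | RMS before excluding 5 points |
|---|---|---|
| 400 | 3.04–3.16 | 3.19–3.73 |
| 720 | 3.02–3.09 | 3.11–3.43 |
| 3,000 | 3.01–3.02 | 3.03–3.11 |

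The same count of points matters less as n grows. The same proportion of points gives the same change at any n.

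**The case against.** **The flag only prompts a review.** This is correct. Item 13d removes nothing automatically, and a reader who infers that every large error is dropped goes beyond the text. But the text does provide for exclusion after the review, and it states no test for it.

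**Flagged points are often artefacts.** This has force. Samples are drawn on plateaus held stable (item 7), so successive errors are likely to be correlated, and a lone jump of 5 or more from both neighbours may well be an artefact. A device with a constant bias has no such jumps, so criterion 2 mainly concerns isolated outliers. A reader might infer that many flags fall on ordinary readings. That depends heavily on treating errors within a session as independent, which the plateau design makes doubtful, and the protocol gives no correlation. No share of flags can be claimed.

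**The reviewer sees more than the bias.** Items 11, 13a and 13b provide perfusion signals, a raw PPG, ECG and arterial waveforms, reference SpO2 and calculated saturation. These could supply an independent cause, but 13d does not tie exclusion to them.

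**The criteria rest on long experience.** The earlier sessions support the flag thresholds. They give no ground for excluding a flagged point.

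**The analysis plan may settle this.** Adjudication details often belong there, and that plan is not at hand. But the protocol itself fixes who excludes and on what basis, so the point concerns a rule that is stated, not one left out.

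**Conclusion.** The concern holds on the text. All three flags in 13d are functions of the study outcome, and exclusion then needs no cause other than the reviewer's instruction. A reading can therefore leave the analysis because its error is large. Where that reading is true device error and exceeds the device's RMS error, reported accuracy becomes too favourable.

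The wording permits this; it does not show that it happens. Nor does it settle whether other points in a flagged session may be removed. The flag attaches to the session and the text speaks only of data points, so a reader might infer that exclusion reaches beyond the reading that raised the flag. The phrase is ambiguous and does not establish that.

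The real effect is unknown. At the assumed 400 points and retained RMS of 3.0, the illustration gives a gain in apparent accuracy of 0.04 to 0.16 for one excluded point and 0.19 to 0.73 for five. It rests on the assumed metric, retained RMS and number of points. This should be fixed: the fault is clear and the repair is cheap.

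**What to change.** Keep the three criteria as a prompt to check, and reword the exclusion sentence of 13d, for example:

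> A flagged test-device point is excluded from the primary analysis only for a documented cause that does not rest on its bias: analyser disagreement; SaO2 or reference instability; a probe or signal fault noted at the time or visible in recorded signals such as perfusion index, PPG or arterial waveform; or a transcription error against the source record. All other points are kept. The reason for each exclusion is recorded.

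Report accuracy with and without the manual exclusions, stated here or in the analysis plan.

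The cost is an exclusion log and one extra analysis run, with no new participants. A brief note of probe faults during the session would help. Item 13 describes none, display video is taken only in some cases ("For some studies, the protocol may video record the hands and/or wrists through the study period"), and item 11 concedes limits in using a neighbouring finger to approximate perfusion at the test site. The downside is that artefacts with no recorded cause stay in the primary figure, so reported accuracy may be slightly less favourable. The report with and without exclusions shows both figures.
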